7.5 Efficacy

Efficacy endpoints are evaluated for treated subjects by as-randomized treatment arm during the treatment period through a specific analysis week. Measurements obtained on treatment and before or on the analysis week date (see [Section 8.2](#)) will be included.

7.5.1 Primary Efficacy Endpoint: Proportion of Subjects with Plasma HIV-1 RNA < 40c/mL at the Week 24 Snapshot

The primary efficacy endpoint is the proportion of subjects with plasma HIV-1 RNA < 40c/mL at the Week 24 snapshot. The primary analysis will be based on a modified ITT (mITT) approach. A sensitivity analysis will be conducted using an observed values approach. The two approaches will be implemented as follows:

- Modified ITT: The numerator will be based on subjects with plasma HIV-1 RNA < 40c/mL at Week 24. The denominator will be based on all treated subjects.

- Observed values: Similar to the mITT approach, the numerator will be based on subjects with plasma HIV-1 RNA < 40c/mL at Week 24. However, the denominator will be based on treated subjects with plasma HIV-1 RNA at Week 24.

Response rates will be tabulated by treatment arm with exact (Clopper-Pearson) binomial 95% confidence intervals.

This endpoint is assessed with the snapshot algorithm. The snapshot algorithm is described in detail in Appendix 1 of the CDER (2013) draft guidance¹ on developing antiretroviral drugs (see also [APPENDIX 1](#) of this SAP). If the draft guidance is superseded, and development timelines permit any needed changes, the instructions from the new guidance should be followed.

The main principle of the snapshot analysis is that the primary efficacy endpoint is intended to be primarily a virologic endpoint and not a clinical endpoint. The snapshot algorithm follows a “Virology First” hierarchy. The hierarchy for assessing percentages is “HIV-1 RNA < Limit of Detection” or “HIV-1 RNA ≥ Limit of Detection” first for any given time window followed by reasons for “No Virologic Data in the Window”.

The snapshot approach algorithm is based on the event occurring within a visit window which is outlined in [Section 8.1](#).

Optimized Background Therapy (OBT) Substitutions

Changes in background therapy are not allowed per protocol. Subjects who do change their dose for TDF in the event of treatment-limiting renal toxicity will be considered virologic failure if they have HIV-1 RNA > 40 at the time of the change.

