8.1.2 On-Treatment Parameters

Time is measured from the first dose of study therapy.

On-treatment parameters are derived from measurements after the start of study therapy through the last dose of study therapy plus 4 days for efficacy, biomarkers and outcomes research scales, plus 10 days for resistance parameters and plus 30 days for safety.

For the primary and secondary efficacy endpoints of proportion of subjects with plasma HIV-1 RNA < 40c/mL at Weeks 24, 48 and 96, the snapshot algorithm and related window definition will be applied. The snapshot windows shown in the [Table 8.1.2-1](#) below differ from those proposed by the FDA by 1 day. The FDA windowing appears to have the first study day as Day 0, while the table below has the first study day as Day 1.

The windows for other parameters are based on the midpoint between planned study visits. For analysis through Week 96, the visit windows are presented in the following table:

Table 8.1.2-1: Visit Windows

Visit	Target Day	HIV-1 RNA (Snapshot Algorithm)	Other Parameters
B/L	1		≤ 1
2	15		2 - 21
4	29		22 - 43
8	57		44 - 71
12	85		72 - 99
16	113		100 - 141
24	169	127 - 210 (18-30 wks)	142 - 197
32	225		198 - 253
40	281		254 - 309
48	337	295 - 378 (42-54 wks)	310 - 379
60	421		380 - 463
72	505		464 - 547
84	589		548 - 631
96	673	631-714 (90-102 wks)	632 - 715

Study days are calculated as:

- Measurement date - first date of study therapy + 1 day, if measurement date is on or after start date of study therapy.
- Measurement date - first date of study therapy, if measurement date is before start date of study therapy.

Weeks are study days divided by 7.

The following conventions are used to select the value to be used in the analysis:

- HIV-1 RNA: analysis of the proportion of subjects with plasma HIV-1 RNA < 40c/mL at Week 24, 48 and 96 use the last plasma HIV-1 RNA value in the pre-defined visit window following the snapshot algorithm. For all other analyses or summaries of HIV-1 RNA, the value in the visit window that is closest to the target day of the planned visit (as determined by the absolute differences in days between the planned visit and the assessment date) will be used. In case of ties between observations located on different sides of the target day, the earlier assessment will be used. In case of ties located on the same side of the target day

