APPENDIX 1 SNAPSHOT ALGORITHM

The snapshot algorithm is described in detail in Appendix A of the CDER (2013) draft guidance on developing antiretroviral drugs¹. If the draft guidance is superseded, and development timelines permit any needed changes, then the instructions from the new guidance should be followed.

In some sections of the draft guidance, the responder cutoff is listed as HIV-1 RNA “< 50copies/mL”. This is a carryover from earlier days when the assay limit of detection was 50. Currently approved assays have lower limits. Hence, in implementing the snapshot algorithm, the assay limit of detection will replace the HIV-1 RNA limit of “< 50copies/mL”.

The analysis visit windows that appear in Table A of the draft guidance (line 1205) appear to use Day 0 as the start date. Windows that use Day 1 as the start date are in the following table.

Table 9-1: Snapshot Algorithm Analysis Visit Windows

VISIT	Window in Weeks (Weeks indicate end of study week)	Days (Inclusive of start & end points)
Week 24	18 through 30	127 through 210
Week 48	42 through 54	295 through 378
Week 96	90 through 102	631 through 714

Each snapshot analysis includes a summary of virologic outcomes at an analysis visit (e.g., Week 24) that has the same format as Table B (line 1209) of the draft guidance.

Each snapshot analysis may also include a summary of expanded virologic outcomes at an analysis visit. This summary has a similar format to Table B, but also displays the 95% CI for the response category “HIV-1 RNA < 40c/mL”, and breaks down the failure category “HIV RNA ≥ 40c/mL” into 4 subcategories. Virologic outcomes are summarized according to the following categories:

- HIV-1 RNA < 40c/mL
- HIV-1 RNA ≥ 40c/mL
 - HIV-1 RNA ≥ 40c/mL in Week 24 window
 - Discontinued study/study drug due to lack of efficacy. This includes subjects who discontinued study therapy due to lack of efficacy at any time from Day 1 through the Week 24 window if this resulted in no on-treatment HIV-1 RNA in the window.
 - Discontinued study/study drug due for other reasons. This includes subjects with last on-treatment HIV-1 RNA ≥ 40c/mL who discontinued study therapy due to any reason except AE, death and lack of efficacy at any time from Day 1 through the Week 24 window if this resulted in no on-treatment HIV-1 RNA in the window.

- No virologic data in Week 24 window

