2. FINAL ANALYSIS

Per the company decision to end this study prior to all subjects reaching the primary endpoint, a simplified approach for the final report has been proposed by the project team. Hence the final analyses for AI468048 study as described in this appendix will be performed on subjects who were enrolled into this study, regardless of study stage, and will supersede what have been previously stated in the finalized BMS RAP Version 2.0. In addition, due to the GCP non-compliance of Site $\frac{PP}{D}$ ([name] in Chile) with ICH GCP E6 (R2) Guidelines, data obtained from this GCP non-compliant site will not be included in the final analyses (e.g., summary tables of selected efficacy and safety data); however, subject data listings will include all subjects enrolled in this study. Subject data listings for the GCP non-compliant Site $\frac{PP}{D}$ will also be provided.

The details of the final reporting and analysis plan are described as below:

1) Analysis Populations

Due to the GCP non-compliance of Site $\frac{PP}{D}$ data obtained from this GCP non-compliant site will be excluded in the final analyses.

Populations for Analyses for this synoptic report are defined as follows:

- Enrolled subjects are those who signed an informed consent form and were assigned a Patient Identification number (PID).
- Randomized subjects are enrolled subjects who received a treatment assignment from the IVRS and will be used in subject data listings as specified.
- Modified Randomized Subjects are enrolled subjects who received a treatment assignment from the IVRS, excluding subjects from Site $\frac{PP}{D}$. The modified randomized subjects will be used to assess subject disposition.
- Treated Subjects are randomized subjects who received at least 1 dose of study therapy and will be used in subject data listings as specified.
- Modified Treated Subjects are randomized subjects who received at least 1 dose of study therapy, exclude subjects from Site $\frac{PP}{D}$. Modified treated subjects will be used to assess demography and baseline characteristics,

protocol deviations, exposure, concomitant medication, efficacy, resistance and safety data.

- Pharmacokinetic (PK) population is defined as all treated subjects who have any available concentration-time data. The evaluable PK population is a sub-population including all treated subjects who have adequate PK profiles.

2) Demographic and baseline characteristic

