This report includes the analyses of demographics, baseline characteristics, and baseline resistance data based on Modified Treated Subjects population. Subject data listings will be based on Treated Subjects population.

The detailed outputs for demographic and baseline characteristic data are listed in the Section 3.1 of List of Displays for Study Population.

3) Simplified report on primary efficacy endpoint

Selected summaries and analyses on primary efficacy endpoint will be performed for this final analysis, based on Modified Treated Subjects population. Subject data listings will be based on Treated Subjects population.

The detailed outputs for primary efficacy endpoint data are listed in the Section 3.2 of List of Displays for Efficacy.

4) Secondary and Exploratory Efficacy Endpoints

Analyses for secondary and exploratory efficacy endpoints, including pharmacokinetic and quality of life endpoints, will not be performed except for HIV-1 RNA, CD4+ counts, and drug resistance endpoints (see additional details in Section 3.4, Virology) which are subject to availability of the data and will be analyzed based on Modified Treated Subjects population. There will be no subgroups and no multivariate analysis performed for secondary and exploratory efficacy endpoints for this final analysis. Subject data listings based on Treated Subjects population except PK data which will be based PK population.

The detailed outputs for primary secondary and exploratory efficacy endpoints are listed in the Section 3.2 of List of Displays for Efficacy.

5) Safety displays

Final safety analysis will be summarized based on Modified Treated Subjects population; however, subject data listings will be based on Treated Subjects population. Subject data listings will be based on Treated Subjects population.

The detailed outputs are listed in the Section 3.3 of List of Displays for Safety.

6) Virology

HIV drug resistance data will be summarized based on Modified Treated Subjects population. Subject data listings will be based on Treated Subjects population.

The detailed outputs for HIV drug resistance data are listed in the section of List of Display for Virology.

7) General

The display for TLFs will be based on BMS shells and will not utilize HARP for SAC.

The list of displays has been updated as shown below.

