3.2.1. Tables

Number	Title	BMS Table number/File Name/BMS Template
2.1	Detailed Summary of HIV-1 RNA < 40 c/mL Proportion of Responders at Week 24 Snapshot Modified Treated Subjects	Table S.5.1.1A / rt-vl-resp40w24s1.lst / SS_VL_T_001
2.2	Summary of HIV-1 RNA < 40 c/mL Proportion of Responders by Scheduled Assessments Over Time Modified Treated Subjects (Observed) ¹	Table S.5.1.1E / rt-vl-resp40w24obssubgs1.lst / SS_VL_T_003 (By Weeks 24, 48, and 96 instead of By Subgroup)
2.3	Summary Statistics for Values and Change from Baseline Over Time CD4 Cell Count (cells/uL) Modified Treated Subjects (Observed) ¹	Table S.5.7.1A / rt-lb-cd4s1.lst / SS_VL_T_006 (Without “By Subgroup”)
2.4	Summary Statistics for Values and Change from Baseline Over Time CD4 Cell Percentage Modified Treated Subjects (Observed) ¹	Table S.5.8.1A / rt-lb-cd4pcts1.lst / SS_VL_T_006 (Without “By Subgroup”)

Number	Title	BMS Table number/File Name/BMS Template
---------------	--------------	--

1 Add the following footnote to the tables 2.2-2.4:

Note: Modified Treated Subjects (Observed): Consisting of subjects in the Treated Subjects Population excluding subjects who have no HIV-1 RNA result data in the assessment visit windows due to discontinuation and who discontinued on or after the date of site notification of study termination by the sponsor [October 10, 2016], will be used to evaluate efficacy in a sensitivity analysis.

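### Final Table 2.1 has no sponsor-termination category, so subjects stopped by the company with no Week 24 RNA count as non-responders, and some of them as virologic failures

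*SAP*

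**What the plan says.** The appendix dated 9 November 2017 replaces the SAP's final analysis with a simplified one. Its section 2 gives the reason: "Per the company decision to end this study prior to all subjects reaching the primary endpoint". Item 1 of that section defines the analysis population: "Modified Treated Subjects are randomized subjects who received at least 1 dose of study therapy", less the GCP non-compliant site. Nothing else is removed. Item 3 assigns this population to the primary endpoint: "Selected summaries and analyses on primary efficacy endpoint will be performed for this final analysis, based on Modified Treated Subjects population".

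The display is Table 2.1 in section 3.2.1 of the appendix, "Detailed Summary of HIV-1 RNA < 40 c/mL Proportion of Responders at Week 24 Snapshot Modified Treated Subjects", on shell SS_VL_T_001. The rules behind it are in the SAP:

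- Section 7.5.1, for the modified ITT response rate: "The denominator will be based on all treated subjects".
- Section 8.1.2: the Week 24 snapshot window is Days 127 to 210.
- Appendix 1: subjects "who discontinued study therapy due to any reason except AE, death and lack of efficacy at any time from Day 1" through the window, with no on-treatment RNA in it and a last value of 40 c/mL or more, form a subcategory of HIV-1 RNA >= 40 c/mL. If the last value was below 40 c/mL, they fall under no virologic data.

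The shell in section 4.5 of the Data Presentation Plan repeats both rules in footnotes D and F. It places D under the number of virologic failures.

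Section 3.2.1 of the appendix also carries a footnote for Tables 2.2 to 2.4. It removes subjects who have no RNA in the visit window because they discontinued and who did so on or after 10 October 2016, when sites were told of the termination. It calls the result a sensitivity analysis. Table 2.1 is not covered by it.

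**The concern.** A company decision to stop a study carries no information on whether a regimen suppresses virus, and SAP section 7.5.1 describes the snapshot endpoint as primarily virologic. Yet someone stopped at Week 8 with RNA still falling, but not yet below 40 c/mL, would be tabulated in the same block as subjects whose treatment failed. Someone already suppressed when stopped would be a non-responder too.

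Two results in the primary table are affected: the Week 24 response proportion with its exact interval, and the virologic failure count. The footnote to Tables 2.2 to 2.4 shows that the plan recognises the problem, but the remedy does not reach the primary table.

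**Working it through.** **Inputs.** Expected response p = 80%, 40 subjects per arm and an exact 95% interval of roughly 64% to 91% (SAP section 5). The window and classification rules are as set out above. The share f of an arm stopped by the termination with no window RNA is not in the documents, so a range is assumed.

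**The plan's own figure.** The Clopper-Pearson interval for 32/40 is 64.4% to 90.9%, which reproduces the stated interval.

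**Classification in Table 2.1 of a subject stopped by the sponsor:**

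| RNA status | Row | Responder | In denominator |
|---|---|---|---|
| Value inside Days 127-210 before stopping | Classified on that value | By value | Yes |
| None in window, last value >= 40 c/mL | Virologic failure, row D | No | Yes |
| None in window, last value < 40 c/mL | No virologic data, row F | No | Yes |

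The first group is unaffected. The other two make up f.

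**Effect on response.** If those stopped would have responded at rate p, the expected Table 2.1 rate is p x (1 - f):

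- f = 5%: 0.80 x 0.95 = 76%
- f = 10%: 0.80 x 0.90 = 72%
- f = 20%: 0.80 x 0.80 = 64%
- f = 25%: 0.80 x 0.75 = 60%

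In counts, for an arm of 40:

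| Stopped, no window RNA | Table 2.1 rule | Stopped subjects removed |
|---|---|---|
| 5 | 28/40 = 70.0% (53.5 to 83.4) | 28/35 = 80.0% (63.1 to 91.6) |
| 10 | 24/40 = 60.0% (43.3 to 75.1) | 24/30 = 80.0% (61.4 to 92.3) |

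**Effect on the failure count.** If a fraction g of those stopped had a last value of 40 c/mL or more, row D gains n x f x g subjects because of the termination alone. With n = 40 and f = 12.5%, 40 x 0.125 = 5 subjects are stopped, so between 0 (g = 0) and 5 (g = 1) are added as failures. The documents do not give g.

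**Effect on arm differences.** With equal f in both arms the difference shrinks by the same factor. A 20-point difference becomes 20 x 0.90 = 18 points at f = 10% and 20 x 0.75 = 15 points at f = 25%.

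**The case against.** The strongest reply is that the appendix has largely dealt with this. Table 2.2 gives the Week 24 proportion below 40 c/mL under a rule that removes subjects without window data who stopped on or after 10 October 2016. Table 2.1 keeps the pre-specified population and the tabular format that SAP section 7.5.1 requires. Changing the primary population in November 2017, 13 months after the notification and in an open-label trial, would itself be a post hoc choice. The misclassification is also partly visible: row D is separate from the row for RNA >= 40 c/mL in the window, and Listing 7 gives each subject's discontinuation day and reason. The trial is one of estimation, the futility test is not among the final efficacy tables, and no decision rule in the appendix rests on Table 2.1. Finally, f may be small.

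Most of this stands. It argues for leaving the population of Table 2.1 alone and against any claim about the actual size of the bias. It does not answer three points. Table 2.2 uses shell SS_VL_T_003, which shows responders and an interval only, so no listed table corrects the failure count. Row D pools sponsor termination with every other stop not due to an AE, death or lack of efficacy. And the footnote starts from the Treated Subjects Population while the table titles say Modified Treated Subjects; read literally, it readmits the excluded site.

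**Conclusion.** The point holds as a defect of classification and presentation in Table 2.1. For any f above zero and a non-zero response rate, the Week 24 response is lowered by the factor (1 - f), and every sponsor-stopped subject without window RNA whose last value was 40 c/mL or more adds one virologic failure. At the planned 80% this is 0.8 percentage points of response per 1% of an arm so stopped. That figure assumes that those stopped would have responded like the rest.

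A reader might infer more than the documents support:

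- *That no termination-adjusted rate is planned.* Table 2.2 gives one.
- *That response will be reported at 72% or 64%.* These are illustrations, because f is not stated. That 64% coincides with the lower limit of the planned interval means nothing; that limit describes precision at 40 per arm.
- *That the headline should be restricted to subjects whose Day 210 fell by 10 October 2016.* This means a first dose on or before 15 March 2016. Day 127 falls on 10 October for a first dose on 6 June, and the Day 169 target for one on 25 April. The restriction would therefore discard subjects whose Week 24 RNA was already observed, and it would replace the pre-specified population.

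**What to change.** In Table 2.1, add a row for no virologic data because the sponsor terminated the study. It should hold subjects with no window RNA who stopped because of the termination on or after 10 October 2016, with counts per arm. State that these subjects never enter the HIV-1 RNA >= 40 c/mL block.

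Beside the full Modified Treated rate, show the Week 24 rate and exact CI with the subjects in that row removed from the denominator, using the appendix's existing 10 October 2016 rule. Correct the footnote to Tables 2.2 to 2.4 so that it starts from Modified Treated Subjects.

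The cost is some appendix wording, one table row and one additional rate. The adjusted rate rests on fewer subjects, so its interval is somewhat wider than planned: 63.1% to 91.6% for 28/35 against 64.4% to 90.9% for 32/40. No observed Week 24 outcome is lost, and the pre-specified rate stays in view.

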3. LIST OF DISPLAYS

The data displays will be based on the BMS shell as specified in the column of BMS Table number/File Name/BMS Template, where applicable. The details information on BMS shell can be found in the Analysis Data Presentation Plan revision 2.0 for this study.

The following data display numbering will be applied for RAP generated displays:

Section	Tables
Study Population	1.1 to 1.5
Efficacy	2.1 to 2.4
Safety	3.1 to 3.46
Virology	4.1 to 4.9
Section	Listings
ICH Listings	1 to 26
Other Listings	27 to 44

3.1. Study Population

3.1.1. Tables

For Table and listing displays, Treated Subjects, Modified Treated Subjects, Randomized Subjects, and Modified Randomized Subjects populations will be used as specified below.

Number	Title	BMS Table number/File Name/BMS Template
1.1	End of Study Subject Status Summary Modified Randomized Subjects	Table S.2.1.1B / rt-ds-status1.lst / GS_DS_T_X_005

Number	Title	BMS Table number/File Name/BMS Template
1.2	Populations for Analysis Summary	Table S.2.1.1C / rt-dm-populations1.lst / SS_DM_T_002
1.3	Demographic Characteristics Summary Modified Treated Subjects	Table S.3.1.1 / rt-dm-summarys1.lst / GS_DM_T_X_002
1.4	Summary of Baseline Disease Characteristics Modified Treated Subjects	Table S.3.2.1 / rt-dm-diseases1.lst / SS_DM_T_004
1.5	Summary of Baseline Physical Measurements Modified Treated Subjects	Table S.3.3.1 / rt-pm-bsls1.lst / GS_PM_T_X_001

3.1.2. ICH Listings

Number	Title	BMS Table number/File Name/BMS Template
1	End of Study Subject Status Randomized Subjects	Appendix 2.1.1B / rl-ds-statuss1.lst / GS_DS_L_X_005
2	Randomization Scheme and Codes Randomized Subjects	Appendix 1.9.1 / rl-ds-randcode.lst / SS_DS_L_001
3	Subjects Excluded from Analysis Treated Subjects	Appendix 2.2.1 / rl-dm-excls1.lst / SS_DM_L_001
4	Listing of Relevant Protocol Deviations Randomized Subjects	Table S.2.3.1B / rl-pd-rels1.lst / SS_PD_L_001
5	Demographic Characteristics Treated Subjects	Appendix 3.1.1A / rl-dm-demchars1.lst / GS_DM_L_X_001

Number	Title	BMS Table number/File Name/BMS Template
6	Non-Study Medication Previous and Concomitant Medications Treated Subjects	Appendix 4.2.1 / rl-cm-meds1.lst / GS_CM_L_X_006

3.1.3. Other Listings

Number	Title	BMS Table number/File Name/BMS Template
27	Listing of Batch Numbers Treated Subjects	Appendix 1.7.1 / rl-ex-batch.lst / SS_EX_L_001
28	Summary of Baseline Disease Characteristics Subjects Enrolled but Not Randomized	Appendix 3.2.1A / rt-dm-diseasenrands1.lst / SS_DM_T_004
29	Listing of HIV Disease Characteristics Treated Subjects	Appendix 3.2.1B / rl-dm-diseases1.lst / SS_DM_L_002
30	Physical Examination Treated Subjects	Appendix 3.4.1 / rl-pe-lists1.lst / GS_PE_L_X_001
31	General Medical History Treated Subjects	Appendix 3.7.1 / rl-mh-list1.lst / GS_MH_L_X_001

